### **Endpoint: Number of Visits**

A descriptive summary of patient visits (Total, outpatient visits, emergency visits, and hospitalization) during the entire study period will be provided, both COPD related and non-COPD related visits will be presented.

A summary by season for COPD-related visits will also be provided, the definition of season is:

- Spring (Mar, Apr, May)
- Summer (Jun, Jul, Aug)
- Autumn (Sep, Oct, Nov)
- Winter (Dec, Jan, Feb)

The total follow-up period (year) and a summary of crude rate of COPD related and non-COPD related visits and the subcategory visits will be provided in a same table. The total follow-up and crude rate are defined as:

$$Total\ Followup\ Time = \sum (Last\ Visit\ Date - First\ Visit\ Date + 1)$$

$$Crude\ Rate = \frac{Sum\ of\ Number\ of\ Visits}{Total\ Followup\ Time\ (year)}$$

### **Endpoint: Direct Medical Costs associated with COPD**

A descriptive summary of overall direct medical costs associated with COPD during the entire study period will be provided. Total cost and subcategory cost, as well as the insurance/out-of-pocket information will also be presented in the summary.

A summary by season for total cost will also be provided. The definition of season is the same with the definition in “Number of Visits” section.

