#### 10.1.2. Study Design Considerations

This is a longitudinal study in subjects with COPD and controls. The follow-up period is 2.5 years with scheduled clinic visits at study entry, 6 months, 18 months, and 30 months.

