where  $\hat{\sigma}_p^2 = \hat{\sigma}_\beta^2 + 12(P - 1)\hat{\sigma}^2 / [D^2 P(P + 1)]$ ,  $r = N_2/N_1$ , and  $N_1$  and  $N_2$  are the sample sizes associated with each of the two groups.

In this study, it is planned to collect  $P=4$  measurements of  $FEV_1$  over  $D=2.5$  years. One of interest is an estimate of the rate of decline in  $FEV_1$  between subjects GOLD I and II.

Under the above assumptions with 95% confidence and a 25% drop out, the following table gives sample sizes necessary to attain the levels of precision of Gold I vs. Gold II comparison.

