### **2.2.2. Additional information for other endpoints**

Treatment pattern will be analysed in baseline (up to 90 days prior baseline to baseline), 0-6m, 6-18m and 18-30m.

HRU data will be analysed in total and by season, as defined in [14.2](#) .

Unless otherwise specified, the other endpoints will be analysed by visits.

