## **14.2. Health resource utilization (HRU)**

The analysis of healthcare resource utilization/cost will be performed in HRU population based on data captured in HIS. Study scheduled visit information is not captured in the database and will not be derived. All the “visit” mentioned in this chapter refers to the information collected from database (i.e. the patient visits a hospital), instead of study scheduled visits (V1-V4).

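### COPD cost is planned only as a total with no person-time denominator, so mean cost is understated wherever cost capture stops at withdrawal or loss to follow-up

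*SAP*

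**What the plan says.** In SAP 14.2, under direct medical costs, "A descriptive summary of overall direct medical costs associated with COPD during the entire study period will be provided". The next sentence extends this to components and payer: "Total cost and subcategory cost, as well as the insurance/out-of-pocket information will also be presented in the summary". Total cost is also split by season. SAP 2.2.2 agrees: "HRU data will be analysed in total and by season". None of these places gives an annualised cost, a person-time denominator or a rule for participants seen for less than the full period. The default summary in SAP 5.4 is n, mean, SD, median and range.

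The visits endpoint just above is treated differently. Besides a raw count it gets "The total follow-up period (year) and a summary of crude rate of COPD related and non-COPD related visits", the rate being summed visits over summed follow-up in years. Protocol 10.2.2 likewise puts count endpoints on a person-year basis.

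On data source, "The analysis of healthcare resource utilization/cost will be performed in HRU population based on data captured in HIS". The HRU population in SAP section 4 leaves out five sites but sets no minimum follow-up. On follow-up, Protocol 10.1.2 says "The follow-up period is 2.5 years with scheduled clinic visits at study entry, 6 months, 18 months, and 30 months", and Protocol 10.1.3 sizes the study "with 95% confidence and a 25% drop out". SAP 17.5.2 and 17.6.1 keep what was collected before loss or withdrawal and carry available planned data into the summary tables.

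**The concern.** A total over the study is comparable between participants only if each was observed for the same time. The plan expects unequal times and retains early leavers, so a participant whose cost record stops at Month 3 would count in the mean exactly as one followed to Month 30. The visits endpoint shows that the plan recognises unequal follow-up, and no reason is given for treating cost otherwise.

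Direct medical cost is a named endpoint of the third objective, and Protocol 5.4 wants the economic impact for different groups of COPD patients. At stake are the level of the reported cost and, if groups are compared and leave at different rates, the comparison itself.

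**Working it through.** **Inputs**
- Planned follow-up T = 2.5 years (Protocol 10.1.2).
- Dropout d = 25% (Protocol 10.1.3), the only dropout figure in the documents. It applies equally to GOLD I and II.
- Assumed: constant yearly cost, cost capture that ends at study exit, and a mean leaving time t of 0.5 years (all at Month 6), 1.25 years (uniform) or 1.5 years (all at Month 18).

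**The plan's own figures.** No cost figure is planned, so the check is on the calculation that carries the dropout.
- σp = √[3.8² + 12 × 3 × 233² / (2.5² × 4 × 5)] = 125.1, as stated.
- Completers per grade for a half-width of 15 mL/year: 1.96² × 125.1² × 2 / 15² ≈ 535, against 525 stated. At 525 the half-width is 15.1, so the figures agree to about 2%.
- 525 / 0.75 = 700 and 1,700 × 0.75 = 1,275, both as stated.

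**Shortfall in mean total cost.** The share of full-period cost observed is (1 − d) + d × t/T.

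| Leaving pattern, d = 25% | Share observed | Shortfall |
|---|---|---|
| All at Month 6 | 0.75 + 0.25 × 0.5/2.5 = 0.80 | 20% |
| Uniform | 0.75 + 0.25 × 1.25/2.5 = 0.875 | 12.5% |
| All at Month 18 | 0.75 + 0.25 × 1.5/2.5 = 0.90 | 10% |

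Under uniform leaving, mean observed time is 0.875 × 2.5 = 2.19 years. For scale only, take the background figure of RMB 20,107.58 per patient per year (Protocol section 3). The full-period cost would be 50,269 and the mean total seen 43,985, which divided by 2.5 reads as 17,594 per year. Summed cost over summed observed time returns 20,107.58.

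**Two groups with the same true yearly cost.** The dropout pairs with unequal values are assumed.

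| Dropout | Ratio of mean totals, uniform leaving | Range, Month 6 to Month 18 | Per person-year |
|---|---|---|---|
| 25% and 25% | 1.00 | 1.00 to 1.00 | 1.00 |
| 20% and 30% | 0.850/0.900 = 0.94 | 0.90 to 0.96 | 1.00 |
| 15% and 35% | 0.825/0.925 = 0.89 | 0.82 to 0.91 | 1.00 |

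**Can the visits denominator be borrowed?** It sums last minus first visit date plus one day, and SAP 14.2 says that a visit in that chapter is a hospital visit, not a study visit. Read that way, a participant with one hospital visit adds one day and a participant with none adds nothing. With Poisson visits (assumed), the mean span is T × Σ P(n)(n − 1)/(n + 1) over n ≥ 1. At 1, 2 and 4 visits a year this gives 0.87, 1.52 and 2.00 years instead of 2.5, so a rate on that base is inflated about 2.9, 1.6 and 1.25 times. Cost needs a different denominator.

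**The case against.** The strongest counter-argument is that truncation at study exit is not established. Costs come from hospital information systems, which do not stop recording when someone misses Visit 3 or 4. Protocol 8.3 defines loss by missed study visits and does not say that extraction ends. Only withdrawal of consent for future information (Protocol 8.2) clearly ends it, and that is a narrower group. The 25% was also set for completers of spirometry, not for lost cost data. This stands: the percentages are illustrations, and the effect shrinks if capture continues. It does not rescue the text, because SAP 14.2 never defines each participant's cost observation period.

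Cost may also rise before a participant leaves, which would offset part of the shortfall. That stands too.

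A reader might infer three stronger things that the documents do not support:
- **Deaths bias total cost down.** They do not. Nothing is spent after death, so the total to death is complete. Cost per person-year alive is a different quantity, not a correction for death.
- **Severe grades will look cheaper.** SAP 14.2 specifies no by-grade cost table. GOLD grades appear only in section 9.2 of the RAP (amendment 2) in the same file, which SAP amendment 3 follows. No grade-specific dropout is given, and with equal dropout the ratio is 1.00.
- **The cost ordering would reverse.** Even with an assumed 10% against 40% uniform dropout, the ratio is 0.80/0.95 = 0.84, so the order flips only if the true cost ratio is below 0.95/0.80 = 1.19. No cost by grade is given to judge that.

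Nor is a comparison with the annual cost in the background section planned. The study is mainly descriptive.

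**Conclusion.** The point holds in a limited form. As written, SAP 14.2 pools cost over unequal observation times and offers no figure that allows for it, while the neighbouring visits endpoint has one. Where cost capture stops at withdrawal or loss, mean total cost is understated by about 12.5% at 25% dropout, with a range of 10% to 20% by timing of exit. This rests on constant yearly cost and on capture ending at exit; the true shortfall is smaller to the extent that either fails in the ways described. Distortion between groups is possible only where their dropout differs, and its size cannot be derived from the documents. The endpoint is descriptive, so this is a recommended improvement and not a threat to the study's main results.

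**What to change.** In SAP 14.2, keep the totals and add COPD-related cost per person-year beside them for total, subcategory, insurance-paid and out-of-pocket cost, overall and for any group in which cost is tabulated. Compute it as summed cost over summed observation time. Define each participant's observation time as the period over which cost was actually captured: from Visit 1 to the earliest of death, end of hospital-record capture, withdrawal of consent or end of study. State whether capture continues after a participant stops attending study visits. Do not reuse the visits formula. Where capture ends at study exit, the study duration already defined in SAP 6.1 (final visit minus Visit 1 plus one day) can serve.

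A total restricted to Visit 4 completers is not a substitute, because it drops everyone who died or withdrew and so adds selection.

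The cost is a few lines of SAP text and a link between study dates and the hospital cost data, since SAP 14.2 says that scheduled-visit information is not held in that database. No new data collection is needed if the capture dates can be recovered. The downside is that cost per person-year alive answers a different question from total cost per participant, so both should be shown and labelled.

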## **15. SAFETY ANALYSES**

Adverse Events (AE) will not be captured in the study as no study drug will be given in this study. Study procedure related serious adverse events (SAE) will be recorded.

### **15.1. Adverse Events**

A listing will be provided for all study procedure related SAEs in Full Population.

Death and cause of death in Full Population will be summarized by arm. If no death case is reported, the table will be omitted.

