#### 9.4. Adverse Events

No study drug will be given in this study, only study procedure related serious adverse events (SAE) will be recorded. All SAEs will be collected from the signing of the ICF until the follow-up visit at the time points specified in the SoA ([Table 1](#)).

The investigator is responsible for the detection and documentation of events meeting the criteria and definition of an SAE, provided in this protocol. During the study when there is a safety evaluation, the investigator or site staff will be responsible for detecting, documenting and reporting SAEs.

Adverse Events (AE) will not be captured in the study. It is possible that participants could spontaneously describe potential adverse events that occurred during the course of study visits. As part of the site orientation process, study team members will be trained in the recognition of potentially-reportable adverse events. If an AE (serious or non-serious) or complaint with any specifically named GSK product is reported spontaneously by a subject during the course of the study, the site staff will complete the AE reporting form and transmit the report to the GSK China within 24 hours of being made aware of the AE.

AE is any untoward medical occurrence in a patient or clinical investigation subject, temporally associated with the use of a medicinal product, whether or not considered related to the medicinal product. An AE can therefore be any unfavourable and unintended sign (including an abnormal laboratory finding), symptom, or disease (new or exacerbated) temporally associated with the use of a medicinal product. For marketed

medicinal products, this also includes failure to produce expected benefits (i.e., lack of efficacy), abuse or misuse.

Serious Adverse Event (SAE) is defined as any untoward medical occurrence that, at any dose:

- Results in death,
- Is life-threatening,
- Requires hospitalization or prolongation of existing hospitalization,
- Results in disability/incapacity,
- Is a congenital anomaly/birth defect?
- Other: medical or scientific judgement should be exercised in deciding whether reporting is appropriate in other situations, such as important medical events that may not be immediately life-threatening or result in death or hospitalisation but may jeopardise the subject or may require medical or surgical intervention to prevent one of the other outcomes listed in the above definition. These should also be considered serious.

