## 4. ANALYSIS POPULATIONS

**Table 2. Summary of Study Populations**

Population	Definition / Criteria	Analyses Evaluated
All Screened	
The All Screened Population will consist of all participants who sign the ICF to participate in the clinical trial.
 
Participants in this population will be used for screen failure summary.
	
 
• Study Population
 

Full	The Full Population will consist of all subjects (except subject PPD ) who are enrolled in the study and attend Visit 1, and not withdraw informed consent.	
 
• Study Population
 
• Disease Progression Analyses
 
• Phenotypic Analyses
 
• Treatment Pattern and Healthcare Resource Utilization/Cost
 
• Safety Analyses
 

Sub-cohort	Sub-cohort is a subset of Full population. Subjects who are enrolled in the Biomarker & Digital sub-cohort and who provided at least one additional sub-cohort assessment.	
 
• Study Population
 
• Disease Progression Analyses
 
• Phenotypic Analyses
 
• Treatment Pattern and Healthcare Resource Utilization/Cost
 
• HRCT analysis
 

HRU	HRU is a subset of Full population. The following sites are not feasible to capture data by HIS, thus the patients enrolled from the following sites will be excluded from HRU analysis: 238160, 238222, 237965, 237971, 238155.	
 
• Treatment Pattern and Healthcare Resource Utilization/Cost
 

[figure not shown]
\*: Subject PPD cannot be categorized into either of the study arms (COPD patients, Chronic Bronchitis patients or Healthy Control), thus excluded from the Full population.

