### **6.1. Participant Disposition**

A summary of patient disposition, including screening status, reasons for screen failures and completers of each visit will be provided for the All Screened Population. In addition, the number of participants enrolled by site will be summarized by arm using the Full population.

A summary of the number of participants in each of the analysis set described will be provided.

A summary of study disposition including factors shown in study population schematic (Figure 1 and Figure 2, respectively) will be provided for Full and Sub-cohort Population, respectively.

Duration of study will be summarized by arm in Full Population and Sub-cohort Population in a same table, using mean(sd), median, Q1, Q3, min and max. For any participants, the duration of study is defined as the number of days from enrollment to study completion or study discontinuation, i.e.

$$\text{Duration} = \text{Date of Final Visit} - \text{Date of Visit 1} + 1$$

The “Final Visit” is defined as the last scheduled visit (including exacerbation visit), regardless of Outpatient visits.

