### Adverse Events

Adverse Events (AE) will not be captured in the study as no study drug will be given in this study.

- If an AE (serious or non-serious) or complaint with any specifically named GSK product is reported spontaneously by a subject during the course of the study, the site staff will complete the AE reporting form and transmit the report to the GSK China within 24 hours of being made aware of the AE.

Study procedure related serious adverse events (SAE) will be recorded.

- All SAEs will be collected from the signing of the ICF until the follow-up visit at the time points specified in the Schedule of Activities ([Appendix 2: Schedule of Activities](#))
- The investigator is responsible for the detection and documentation of events meeting the criteria and definition of an SAE, provided in this protocol. During the study when there is a safety evaluation, the investigator or site staff will be responsible for detecting, documenting, and reporting SAEs

Serious Adverse Event (SAE) is defined as any untoward medical occurrence that:

- Results in death,
- Is life-threatening,
- Requires hospitalization or prolongation of existing hospitalization,
- Results in disability/incapacity,
- Is a congenital anomaly/birth defect,
- Other: medical or scientific judgement should be exercised in deciding whether reporting is appropriate in other situations, such as important medical events that may not be immediately life-threatening or result in death or hospitalization but may jeopardize the subject or may require medical or surgical intervention to prevent one of the other outcomes listed in the above definition. These should also be considered serious.
- Possible drug-induced liver injury

See study Pharmacovigilance Plan (sPVP) for details. sPVP will include the following elements to ensure a comprehensive approach to safety event collection and reporting:

- Supplier pharmacovigilance training
- Investigator and site staff pharmacovigilance training
- Safety-specific roles

Adverse Events

• SAEs collection and reporting processes

• SAEs collection forms

• Frequency of data review

• Reporting process and timelines

• Interim reports

• Study-specific PVP monitoring process

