**Microbiome****17.6. Appendix 6: Reporting Standards for Missing Data****17.6.1. Premature Withdrawals**

Element	Reporting Detail
General	
 
Subject study completion (i.e. as specified in the protocol) was defined as completed all scheduled visit and completed exit visit.
 
Withdrawn subjects were not replaced in the study.
 
All available data from participants who were withdrawn from the study will be listed and all available planned data will be included in summary tables and figures, unless otherwise specified.
 
Withdrawal visits will be slotted as per Appendix 3: Assessment Windows or will be summarised as withdrawal visits.
 

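### SAP 15.1 lists procedure-related SAEs in the Full Population only, so under Table 2 an SAE in a screen failure, the one unclassifiable subject or a consent withdrawal reaches no planned safety output

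*SAP*

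**What the plan says.** **Collection.** Protocol 9.4 states: "All SAEs will be collected from the signing of the ICF until the follow-up visit at the time points specified in the SoA". The Adverse Events block of SAP 17.5.2 repeats the starting point: "All SAEs will be collected from the signing of the ICF until the follow-up visit". SAP 15 adds that adverse events in general are not captured, because no drug is given; only SAEs related to study procedures are recorded.

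**Display.** SAP 15.1 plans one output for them: "A listing will be provided for all study procedure related SAEs in Full Population". A table of deaths by arm is also planned, in the same population.

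**Populations (SAP Table 2).** The Full Population takes subjects "who are enrolled in the study and attend Visit 1, and not withdraw informed consent". A footnote deals with one subject who belongs to none of the arms, "thus excluded from the Full population". The All Screened Population takes everyone who signs the consent form, but its use is narrow: "Participants in this population will be used for screen failure summary". SAP 6.1 gives it a disposition summary, in which screening status, failure reasons and "completers of each visit will be provided for the All Screened Population". Safety analyses are assigned to Full.

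**Withdrawn participants.** SAP 17.5.2 keeps and reports what was collected before a subject withdraws consent for disclosure of future information. SAP 17.6.1 says: "All available data from participants who were withdrawn from the study will be listed", subject to a proviso for anything specified otherwise.

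**The concern.** The listing starts from a narrower group than the one in which the events are collected. Consent precedes every study procedure (Protocol Table 1, footnote 2), so a person can undergo a procedure, have a related SAE, and still never be in Full.

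Study-procedure SAEs are the only adverse events this study sets out to record. A reader of the study report will look to this listing for the harm done by study procedures such as blood draws, spirometry, CT scanning and sputum induction. If some consented people are outside it by rule, the listing could be incomplete without showing that it is. No effect estimate is at stake.

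**Working it through.** No arithmetic applies. The check takes each group of consented people and asks whether the 15.1 listing, or any other planned safety output, would show their SAE.

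1. **Enrolled, attended Visit 1, fits an arm, consent not withdrawn.** In Full, so covered.

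2. **Screen failures.** Protocol 6.4 defines them as people who consent but are not then entered. They are therefore not enrolled and not in Full. They are in All Screened, which carries only disposition and screen-failure summaries (Table 2, SAP 6.1). Not covered. Exposure to procedures before failing is possible: the exclusion criteria in Protocol 6.2 allow exclusion on a finding from the first CT scan, and eligibility depends on post-bronchodilator spirometry. It is also limited: CT and sputum induction are for the sub-cohort only, and Protocol 9 lets routine spirometry done before consent serve for screening.

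3. **The subject who fits no arm.** Removed from Full by the Table 2 footnote. Not covered. The stated reason is about arms. That justifies leaving the subject out of by-arm tables, but 15.1 makes only the death table by arm and does not say this of the SAE listing.

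4. **Participants who withdraw informed consent.** Outside Full by Table 2, so not covered by 15.1 as written. The three relevant texts compare as follows:
   - Table 2 speaks of withdrawing informed consent.
   - SAP 17.5.2 speaks of withdrawing consent for disclosure of future information, and keeps the earlier data in the report.
   - SAP 17.6.1 speaks of being withdrawn from the study, and lists all available data unless something else is specified.

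   These may be different kinds of withdrawal, and a listing restricted to Full may count as something else being specified. The SAP does not settle either question, so a programmer cannot tell whether such an SAE should be listed.

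**Size.** The documents identify one subject under group 3. They give no count of screen failures, of consent withdrawals, or of SAEs in any of the three groups.

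**How often screening SAEs would arise.** In the schedule of activities (Protocol Table 1, repeated in SAP 17.2.1), SAE assessment is blank at Screen/Baseline and marked from Visit 2 onward. An SAE in a screen failure would therefore be captured only through the wording that collection runs from consent. Such records are probably few.

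**The case against.** The case for leaving 15.1 alone is reasonable. Protocol 10.2.6 names no population for SAEs, so no protocol requirement is broken. SAP 2.1 declares that populations follow the SAP. Basing safety displays on enrolled participants is defensible in a mainly descriptive cohort with no investigational product. The schedule has no SAE assessment at screening, and Protocol 6.4 lists the minimum screen-failure data without mentioning SAEs. All of this stands, and it keeps the point small. It does not close the gap: collection is still stated to run from consent, and nothing else in the SAP displays an SAE from the three groups.

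A reader might infer two stronger points that the documents do not support.

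- *That the SAP contradicts itself on consent withdrawals.* Table 2, 17.5.2 and 17.6.1 describe withdrawal in different terms, and 17.6.1 carries its own proviso. The texts can be reconciled; the SAP simply does not say how.
- *That the gap is wide because only one of the populations in Table 2 carries safety analyses.* Sub-cohort and HRU are subsets of Full, so a Full listing already covers them. Only All Screened reaches beyond Full.

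**Conclusion.** The point holds as a minor one. Under Table 2, an SAE in a screen failure, in the one unclassifiable subject, or in a participant who withdraws informed consent would appear in no planned SAP safety output. For the third group this is subject to the ambiguity described above.

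The consequence is limited to completeness of the safety listing in the clinical study report. The pharmacovigilance plan (Protocol 9.4) and the investigator's duty to notify the IRB/IEC (Protocol 12.2) still apply, and no estimate changes. It would be wrong to infer that events have been lost: none is shown, and the number may be zero. Nor is the departure from the protocol's Full Population itself a fault, since SAP 2.1 declares it.

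The conclusion assumes that the SAP governs over the appended reporting and analysis plan, which the version history supports. That plan's Full Population, all enrolled subjects attending Visit 1, would have kept the unclassifiable subject and enrolled consent withdrawals, but not screen failures.

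**What to change.** In SAP 15.1, replace Full with All Screened as the population for the procedure-related SAE listing. Add a column that flags anyone outside Full, with the reason: screen failure; not classifiable to an arm; or consent withdrawn, where use of the earlier data is permitted. In Table 2, add this listing to the analyses for All Screened. One sentence there on which withdrawal of consent removes a participant from Full, and how that relates to 17.5.2 and 17.6.1, would end the ambiguity.

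The cost is a few lines of SAP text and a little extra listing work. No protocol amendment, patient or visit is needed, and All Screened is already defined. One check is required: the documents do not show that SAE records for screen failures sit in the clinical database, so the team should confirm that they can be drawn from the existing safety records.
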